5.5 Missing Data Algorithms

In general, missing data will not be imputed unless methods for handling missing data are specified.

5.5.1 Birth Dates

If the date of birth is only partially available, the first of the month will be imputed for any missing days and January will be imputed for any missing months. Imputed dates will not be presented in the data listings.

5.5.2 Medical History Diagnosis Dates

If the onset date of Graves' disease or TED is only partially available, the first of the month will be imputed for any missing days and January will be imputed for any missing months. Imputed dates will not be presented in the data listings.

5.5.3 Adverse Events

For adverse events with incomplete dates, the following rules will be used to impute start and/or stop dates for the sole purpose of determining whether if an AE is treatment emergent. Imputed dates will not appear in the data listings.

For partial or missing AE start dates:

- If day is missing, and the month and year match the month and the year of the first dose date, the day of the first dose date will be imputed and the AE will be considered treatment emergent. Otherwise, the first of the month will be used and the treatment-emergent status will be assessed relative to the dosing start date.
- If the day and month are missing, and the year matches the year of the first dose date, the month and the day of the first dose date will be imputed, and the AE will be considered treatment emergent. Otherwise, January 1 will be used and the treatment emergent status will be assessed relative to the dosing start date.
- If the start date is completely missing, the AE will be considered treatment emergent unless the stop date is complete and prior to the first dose or provides enough partial information to rule out a treatment-emergent status.
- If the stop date is complete and the imputed start date is after the actual stop date, then the start date will be imputed as the stop date and the treatment-emergent status will be assessed relative to the dosing start date.

Any missing intensity assessments for AEs will be imputed as “severe” and any missing relationship to study drug will be considered “related” for summary purposes.

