10.1 Adverse Events

Adverse events will be coded using MedDRA version 24.0. AEs that occur during Screening and prior to dosing on Day 1 will be considered pre-treatment AEs. TEAEs for the double-masked treatment period is defined as AEs with onset date on or after the first dose of study drug during the double-masked treatment period prior to receiving the first dose of TEPEZZA during open-label treatment period for patients who entered open-label treatment period, or through 3 weeks (21 days) after the last dose of study drug during the double-masked treatment period for patients who did not enter open-label treatment period. TEAEs for open-label treatment period defined as AEs with onset date on or after first dose of TEPEZZA during the open-label treatment period through 3 weeks (21 days) after last dose of TEPEZZA during the open-label treatment period. All analyses for TEAEs will be split to TEAEs reported during the double-masked treatment period and open-label treatment period separately. The follow-up AE reporting period begins 3 weeks (21 days) after the last dose of study drug through completion of the follow-up period.

An overall summary of all TEAEs including the number and percentage of patients experiencing at least one occurrence of a TEAE, serious TEAEs, treatment-related TEAEs, treatment-related serious TEAEs, TEAEs resulting in study drug discontinuation, TEAEs of special interest, TEAEs leading to death along with the summary of National Cancer Institute Common Terminology Criteria for Adverse Events (NCI-CTCAE) grade 3 or higher will be provided.

Additionally, AEs and SAEs reported during the follow-up period after each treatment period will be presented by SOC and PT separately.

All AEs, AEs with CTCAE Grade 3 or higher, SAEs, AEs leading to discontinuation of study drug, AE of special interest, and deaths will be presented in separate by-subject listings.

Signs and symptoms associated with Infusion reaction and anaphylaxis will be recorded and included in a by-subject listing.

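### Partial adverse-event start dates have no anchor at the first open-label dose, so some open-label events default to the masked period

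*SAP*

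**What the plan says.** SAP 5.5.3 has one anchor for incomplete AE start dates, the first dose date.

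- **Day missing.** The first dose date is imputed "If day is missing, and the month and year match the month and the year of the first dose date". For every other month: "Otherwise, the first of the month will be used and the treatment-emergent status will be assessed relative to the dosing start date".
- **Day and month missing.** The first dose date is imputed "If the day and month are missing, and the year matches the year of the first dose date"; for any other year, 1 January is used.
- **Stop-date correction.** It applies "If the stop date is complete and the imputed start date is after the actual stop date", and replaces the imputed start with the stop date.
- **Stated purpose.** The imputation is made "for the sole purpose of determining whether if an AE is treatment emergent".

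SAP 10.1 then sets the periods by onset date. For patients who continue, the masked window covers events with onset "prior to receiving the first dose of TEPEZZA during open-label treatment period for patients who entered open-label treatment period". The open-label window covers "AEs with onset date on or after first dose of TEPEZZA during the open-label treatment period through 3 weeks (21 days") after the last open-label dose. The tables follow that division: "All analyses for TEAEs will be split to TEAEs reported during the double-masked treatment period and open-label treatment period separately".

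**The concern.** The boundary that matters for the TEAE tables of a crossover patient is the first open-label dose, and 5.5.3 does not mention it. The first of a month, 1 January or the first masked dose can each fall before that boundary when the true onset fell after it. The event then appears in the masked-period table, which is the randomised safety comparison. For a patient randomised to placebo, a reaction to active drug would be listed as a placebo event. The affected month also contains the first open-label infusion, and Protocol 9.5.3.1.1.5 says infusion reactions are usually associated with the first infusion.

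**Working it through.** The plan gives no figure on this point, so there is nothing to reproduce. The check applies the 5.5.3 rules and then the 10.1 windows.

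**Inputs**
- First open-label dose at Week 24, last at Week 45 (SAP 3.1): 24 × 7 = 168 days after Day 1, then 21 × 7 = 147 days.
- Open-label TEAE window: 147 + 21 days, inclusive = 169 days (SAP 10.1).
- 38 TEPEZZA and 19 placebo patients (SAP 5.1).
- Assumptions: Day 1 uniform over four calendar years (1,461 dates), onset uniform over the window, all eight open-label infusions given. Offsets of 161 and 175 days were also run for the Week 24 visit window.

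**1. Day missing**

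By hand for a 30-day month: a dose on day d leaves 31 − d onset days in that month. Summed over d = 1 to 30 this is 465. Only the 30 days belonging to d = 1 are placed correctly.
- Misplaced within the month: 435/465 = 93.5%. Real calendar: 93.6%. For events on the dose day itself: 96.7%.
- Share of the whole window: 435/30 = 14.5 days; 14.5/169 = 8.6%. Real calendar: 8.7%.
- Range: 0% (dose on the 1st) to 30/169 = 17.8% (dose on the 2nd of a 31-day month).
- Any later month: 0%, because the first of that month already follows the open-label dose.

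Example: Day 1 on 10 January 2022, open-label dose on 27 June 2022. An onset on 30 June recorded only as June 2022 becomes 1 June (masked, wrong). An onset on 7 July recorded only as July 2022 becomes 1 July (open-label, right).

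**2. Day and month missing**

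Two routes lead to the masked period. By hand for a 365-day year, there are 365 × 169 = 61,685 combinations of start day and onset day.
- Onset in the year of the first masked dose, imputed to Day 1: 29 × 169 + (168 + 167 + … + 1) = 4,901 + 14,196 = 19,097, or 31.0%. Every such event is misplaced.
- Open-label dose in the following year, after 1 January, with onset in that year and imputed to 1 January: 167 × 169 = 28,223, or 45.8%.
- Together 76.7%, as in the full calendar run (0% to 100% by start date). The three offsets give the same total.

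**3. Other direction.** The present rule moves no true masked-period event to the open-label period. The stop-date correction only moves a start earlier, so it cannot repair the cases above.

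**4. Size in a table.** One placebo crossover: 1/19 = 5.3 points. One TEPEZZA crossover: 1/38 = 2.6 points. Both are ceilings, because SAP 10.1.1 counts a patient once per term; a patient who already had that term in the masked period adds nothing.

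**5. A bare second anchor at the first open-label dose.** Misplaced open-label events fall to 0% in both cases. But true masked-period events then move to open label: 8.8% with the day missing (8.4% to 9.2% over the visit window) and 76.9% with day and month missing (75.9% to 77.8%).

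**The case against.** The best reply is that 5.5.3 limits its imputation to deciding treatment emergence and never says that the imputed date fixes the period. That is true, but 10.1 defines a TEAE separately for each period by onset date. Either the imputed date sets the period, with the results above, or no rule does; both need the same edit. Reading the first dose date as specific to each period would remove the problem, but 5.5.3 does not say so. Elsewhere the SAP names its second anchor when it wants one (TEPEZZA Study Day in 5.4.1, TEPEZZA Baseline in 5.4.2).

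It is also fair that partial dates should be rare in this interval. Patients are monitored after the infusion, contacted the day after the first two open-label infusions and seen every three weeks; start and stop dates are required in source, and omissions are queried. That limits the likely number of events, but does not settle how they are allocated.

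A reader might infer two stronger things, and the documents support neither. One is that any open-label event with a missing day goes to the masked period; with only the day missing, about 91% of the open-label window is placed correctly. The other is that the error narrows the safety difference. Non-responders of either arm may continue (SAP 3.1), and for those randomised to TEPEZZA the same rule adds events to the masked TEPEZZA column and widens it. The mix of crossovers is not given.

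**Conclusion.** The gap is real and minor. The imputation rule and the period definition use different anchors. The error runs one way between periods, from open-label to masked, but its net effect on the comparison of arms is unknown. It affects about 8.7% of the open-label window when the day is missing and about 77% when day and month are missing, under uniform start and onset dates and full open-label dosing. The ceiling is 5.3 points per placebo crossover for a given term. How often start dates are incomplete is not in the documents, so the effect on the final tables cannot be sized. It can reach the primary safety tables, because SAP 4.2 takes safety data up to the last patient's Week 24 visit, by which time earlier crossovers may already be on open-label drug. No efficacy analysis is affected.

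**What to change.** Add to SAP 5.5.3, before database lock, a rule for patients who enter the open-label period whose partial start date is compatible with both periods:

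1. Assign the period first by the stop date and by the visit or period at which the event was first reported. An event reported at or before the Week 24 pre-dose assessment is masked.
2. Only if these do not settle it, and the known month and year (or year alone) match those of the first open-label dose, impute the first open-label dose date. This takes precedence over the first-dose rule when both doses fall in the same year, which holds for about 54% of start dates (197/365).
3. State that the resulting date also determines the period.

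The order matters: step 2 alone would cause the reverse misplacement shown in the working.

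The cost is a few lines of text and programming. The documents do not describe a field for the visit of first report, so its source must be named. The Week 24 visit label is not enough by itself, because Protocol 9.5.6.2.5 lets AE monitoring continue past the open-label infusion. The remaining downside is that a few true masked-period events with no resolving information may move to open label.

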5.5.4 Medication Dates

For prior and concomitant medications with incomplete dates, the following rules will be used to impute start and/or stop dates for the purposes of determining if a medication is prior or concomitant only. Imputed dates will not be presented in the data listings.

For partial or missing start dates:

- If day is missing, and the month and year match the month and the year of the first dose date, the day of the first dose date will be imputed. Otherwise, the first of the month will be used.
- If day and month are missing and the year matches the year of the first dose date, the month and the day of the first dose date will be imputed. Otherwise, January 1 will be used.
- If the start date is completely missing, the start date will not be imputed. If the stop date is after first dose date, the medication will be considered to be concomitant. If the stop date is prior to the first dose date, the medication will be considered to be prior.
- If the stop date is complete and the imputed start date is after the actual stop date, then the start date will be imputed as the stop date.

[figure not shown]
For partial or missing stop dates:

- For stop dates, if the day is missing, then the last day of the month will be used.
- If the month is missing, then December will be used.
- If the stop date is completely missing, then the latest date available in the dataset for the patient will be used.
- All medications with a missing stop date will be considered as concomitant.

5.6 Multiplicity

If a statistically significant result in favor of TEPEZZA is achieved on the primary efficacy endpoint, the other efficacy endpoints (with the primary analyses defined in the study) will be analyzed in a hierarchical manner to control for multiplicity. For each other efficacy endpoint, TEPEZZA will be tested against placebo at the two-sided 0.05 significance level only if the test statistic was statistically significant in favor of TEPEZZA for the endpoint preceding it in the following hierarchical order:

1. Proptosis responder rate (the percentage of patients with a ≥ 2 -mm reduction from Baseline in proptosis in the study eye, without deterioration [≥ 2 -mm increase] of proptosis in the fellow eye) at Week 24
2. Change from Baseline at Week 24 in the GO-QoL questionnaire appearance and visual functioning subscales

6. Patient Disposition

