3.2.2 Other Efficacy Endpoints

1. The proptosis responder rate (percentage of patients with a ≥ 2 -mm reduction from Baseline in proptosis in the study eye, without deterioration [≥ 2 -mm increase] of proptosis in the fellow eye) at Week 24.
2. The change from Baseline at Week 24 in the GO-QoL questionnaire appearance and visual functioning subscales.

[figure not shown]

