4.3 Follow-up Analysis

The follow-up analysis is planned at the end of the trial after all patients complete the 30-day follow-up period or terminate early from the study during the follow-up period. The follow-up analysis will focus on the open-label treatment period. For the open-label treatment period,

1. Only descriptive summaries will be provided and no statistical modeling or statistical hypothesis tests will be performed.
2. Neither sensitivity nor supplementary analysis will be performed.
3. Analysis results will be presented by the treatment patients received during the double-masked treatment period.

Efficacy analyses are based on data collected from open-label treatment period. Safety analyses are based on data collected from open-label treatment period as well as 30-day follow-up data that are not included in the primary analysis.

5 General Statistical Considerations

The primary efficacy endpoint will be tested at the level of significance of 0.05 two-sided. Other efficacy endpoints will be tested in a sequential order as listed in Section 3.2.2 only when statistical significance is achieved for the primary efficacy endpoint and the other preceding endpoint in the prespecified order is statistically significant at the 0.05 significant level (two-sided).

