9.2.5 Exploratory Analysis

9.3 Other Efficacy Endpoints

Inferential testing on other efficacy endpoints will be made only when the primary efficacy endpoint reaches statistical significance at 0.05 (two-sided) in favor of TEPEZZA. Other efficacy endpoints (with the main analyses defined in the study eye as appropriate) will be analyzed using the ITT analysis set in a hierarchical manner presented in the order in Section 5.6. For each outcome measure, TEPEZZA will be tested against placebo at the two-sided 0.05 significance level only if the test statistic was statistically significantly in favor of TEPEZZA for the outcome measure preceding it in the hierarchical order.

9.3.1 Proptosis Responder Rate at Week 24

The proptosis responder rate is defined as the percentage of patients with a ≥ 2 -mm reduction from Baseline in proptosis in the study eye, without deterioration [≥ 2 -mm increase] of proptosis in the fellow eye at each scheduled visit.

Population	ITT Analysis Set defined as all patients who were randomized in the trial
Endpoint	
Proportion of patients who have achieved the proptosis response rate at Week 24.
 
The proptosis responder rate at Week 24 is defined as the percentage of patients with a ≥ 2-mm reduction from Baseline in proptosis in the study eye, without deterioration (≥ 2-mm increase) of proptosis in the fellow eye at Week 24.

ICE	Discontinued from treatment early
Population-level Summary	Difference (TEPEZZA minus placebo) in proptosis responder rates at Week 24 between the treatment groups

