A patient listing of serum concentration-time data will be presented by visit. Teprotumumab peak and trough (i.e., prior to dose) concentrations will be summarized by visit and ADA status (overall positive vs cumulative negative; only to be performed if more than 2 patients receiving TEPEZZA treatment with a positive ADA observed in the trial) using descriptive statistics. The analyses will be based on the PK analysis set in each treatment period.

Further, the mean and CV% (calculated as 100%*SD/mean) of pre-dose serum concentrations will be provided by visit in the subset of patients who are confirmed ADA positive, NAb positive (if applicable) and ADA negative for each visit. This analysis will be provided for the PK Population.

13. Changes in the Planned Analysis

- To ensure the control of the overall Type I error rate in analyzing multiple efficacy endpoints, the process to test individual efficacy endpoints has been added in the SAP section 5 and section 9, as an addition to the protocol.
- TEPEZZA Baseline is defined in the SAP for analysis relative to baseline in the open-label treatment period.
- TEPEZZA study day is defined in the SAP for analysis relative to first dose date during the open-label treatment period.

- To better characterize GO-QoL, analyses of patients with minimal clinically important change in the GO-QoL subscales will be provided.
- Summary and shift tables for chemistry (excluding glucose) will be based on all records (fasting and non-fasting records).

14. References

Heitjan DF and Little RJA. Multiple Imputation for the Fatal Accident Reporting System. *Journal of the Royal Statistical Society, Series C*. 1991; 40:13–29.

Rubin DB. *Multiple Imputation for Nonresponse in Surveys*. New York: John Wiley & Sons. 1987.

Schenker N and Taylor JMG. Partially parametric techniques for multiple imputation. *Computational Statistics & Data Analysis*. 1996; 22:425-446.

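### Do the two GO-QoL subscales sharing one step of the testing sequence break the type I error control in SAP 5.6?

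*SAP*

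**What the plan says.** SAP section 5 fixes the primary test ("The primary efficacy endpoint will be tested at the level of significance of 0.05 two-sided") and then says "Other efficacy endpoints will be tested in a sequential order as listed in Section 3.2.2". SAP 3.2.2 lists the proptosis responder rate first, and second "The change from Baseline at Week 24 in the GO-QoL questionnaire appearance and visual functioning subscales". SAP 5.6 repeats those two items, the second as "Change from Baseline at Week 24 in the GO-QoL questionnaire appearance and visual functioning subscales", and sets the rule for each: "TEPEZZA will be tested against placebo at the two-sided 0.05 significance level only if the test statistic was statistically significant in favor of TEPEZZA" on the endpoint before it. SAP 9.3 sends the reader back to 5.6, with the endpoints analysed "in a hierarchical manner presented in the order in Section 5.6".

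SAP 13 gives the purpose, "To ensure the control of the overall Type I error rate in analyzing multiple efficacy endpoints", and says that the process was added in sections 5 and 9. SAP 9.3.2, the section on the GO-QoL analysis, is mostly blacked out. SAP 2.2 has five other objectives, but the visible lists in 3.2.2 and 5.6 stop at the second item.

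**The concern.** A fixed sequence controls the overall error because each step carries one hypothesis at full alpha and a failure stops the procedure. The second step here carries two hypotheses, one per subscale. SAP 5.6 speaks of a single test statistic per endpoint and gives no order within the step, no requirement that both succeed, and no split of alpha.

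The open question is whether one positive subscale alone would be a valid claim. If it would, and each subscale is tested at 0.05, the step has two chances to succeed by luck, and the control described in SAP 13 is lost there. If the answer were settled only after unmasking, it could follow the data. Any later step would also lack a clear opening condition.

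**Working it through.** **The plan's own figure.** Inputs from SAP 5.1: 38 and 19 patients, difference 2.0 mm, SD 2.5, two-sided 0.05.

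- Standard error = 2.5 × √(1/38 + 1/19) = 0.702.
- 2.0 / 0.702 = 2.847, and 2.847 − 1.96 = 0.887.
- Power = Φ(0.887) = 0.8125, matching the stated 81%. The noncentral t version gives 0.799.

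**Error at the GO-QoL step.** Suppose both subscale nulls are true and both earlier gates are passed. Let Z1 and Z2 be the two subscale statistics, bivariate normal with correlation r, and c = 1.96. The documents give no r, so a range is assumed.

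- Either may be claimed: 1 − P(|Z1| < c, |Z2| < c).
- Either, counting only results in favour of TEPEZZA: 1 − P(Z1 < c, Z2 < c). The nominal value is 2.5%.
- Both required: 0.05 + 0.05 − P(either).

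| r | Either, two-sided | Either, favouring TEPEZZA | Both required, two-sided |
|---|---|---|---|
| 0 | 9.75% | 4.94% | 0.25% |
| 0.3 | 9.51% | 4.76% | 0.49% |
| 0.5 | 9.07% | 4.54% | 0.93% |
| 0.7 | 8.35% | 4.17% | 1.65% |
| 0.9 | 7.04% | 3.52% | 2.96% |

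At r = 0 the first column is 1 − 0.95² = 0.0975. The both-required error is at most 5% when only one null is true. Testing one subscale and then the other also gives at most 5%. Only the either reading exceeds the level.

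**Chance of reaching the step.** This was simulated with 40,000 trials per setting: 38 against 19 patients, normal changes, and placebo mean 0, −0.48 or −1 mm. A t-test stood in for the MMRM, followed by Fisher's exact test on a reduction of at least 2 mm. Dropout and fellow-eye worsening were left out.

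- 2.0 mm, SD 2.5 (the plan): 0.507 to 0.537.
- 2.0 mm, SD 2.0 (assumed SD): 0.699 to 0.749.
- 3.0 mm, SD 2.0 (both assumed): 0.977 to 0.982.

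**Overall error under the either reading.** This is the gate probability times the step error, taking the GO-QoL tests as independent of the proptosis tests.

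- Plan values, r = 0: 0.507 × 9.75% = 4.9% to 0.537 × 9.75% = 5.2%.
- Plan values, r = 0.5: 0.507 × 9.07% = 4.6% to 0.537 × 9.07% = 4.9%.
- Plan values, r = 0.7: 0.507 × 8.35% = 4.2% to 0.537 × 8.35% = 4.5%.
- 2.0 mm, SD 2.0, r = 0: 0.699 × 9.75% = 6.8% to 0.749 × 9.75% = 7.3%.
- 3.0 mm, SD 2.0, r = 0: 0.977 × 9.75% = 9.5% to 0.982 × 9.75% = 9.6%.

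**What the passages support.** The item joins the subscales with the word and; no visible text offers them as alternatives. Read as a conjunction, both are required. Read as a list inside an ordered procedure, appearance is tested before visual functioning. Both readings hold 5%. The gate condition, "only if the test statistic was statistically significant in favor of TEPEZZA for the endpoint preceding it", governs movement from one endpoint to the next, and GO-QoL is the last visible endpoint. No visible test therefore depends on how this step is passed.

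**The case for a change.** The strongest case for acting is that strong control must hold whatever the true proptosis effect. The figure of about 5% at the planning values is then no defence, because it comes from the sequence often stopping before GO-QoL. The plan itself describes its SD as larger than that seen in the Phase 2 and Phase 3 trials, so a smaller SD is plausible, and at SD 2.0 the either reading gives about 7%. Since 9.3 cites 5.6 for the order, 5.6 is where a reader expects the rule, and stating it would take only a line or two.

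The arithmetic in that case stands, and so does the observation that visible 5.6 is silent. But the excess belongs to a procedure that the plan does not state. To find a fault, one must choose the least natural reading and also assume that the blacked-out GO-QoL text holds no rule. SAP 13 places part of the testing process in section 9, so 9.3.2 is a likely place for it. The lists in 3.2.2 and 5.6 also stop short of the five other objectives, so 5.6 itself may be incomplete in the public copy; that is an inference, as no redaction mark appears there. Text that cannot be seen for these reasons cannot be counted as missing.

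**Conclusion.** No change follows. The visible SAP leaves a detail unstated; it does not set a rule that gives a wrong error rate. The two readings closest to the wording, both required or tested in the order named, keep the step at or below 5%, and an analyst applying a hierarchical procedure would sensibly adopt one of them. The error rises to between 7.0% and 9.75% at the step only if each subscale is tested at 0.05 and either may be claimed, with both nulls true, both gates passed and correlation between 0.9 and 0. At the plan's 2.0 mm and SD 2.5 even that reading gives about 5.2% or less overall; at SD 2.0, or with a 3.0 mm effect as well, it gives more.

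The primary and proptosis responder tests are unaffected on any reading. The conclusion rests on assumed correlations, on a simulation that simplifies the primary analysis, and on the unseen text not prescribing the either rule. If it did prescribe that rule, the concern would hold.
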